### **11.3 Responsibilities of the investigator and IRB/IEC**

The protocol and the proposed informed consent form must be reviewed and approved by a properly constituted Institutional Review Board/Independent Ethics Committee/Research Ethics Board (IRB/IEC) before study start. A signed and dated statement that the protocol and informed consent have been approved by the IRB/IEC must be given to Novartis before study initiation. Prior to study start, the investigator is required to sign a protocol signature page confirming his/her agreement to conduct the study in accordance with these documents and all of the instructions and procedures found in this protocol and to give access to all relevant data and records to Novartis monitors, auditors, Novartis Clinical Quality Assurance representatives, designated agents of Novartis, IRBs/IECs, and regulatory authorities as required. If an inspection of the clinical site is requested by a regulatory authority, the investigator must inform Novartis immediately that this request has been made.

## **11.4 Publication of study protocol and results**

Novartis assures that the key design elements of this protocol will be posted in a publicly accessible database such as [clinicaltrials.gov](http://clinicaltrials.gov). In addition, upon study completion and finalization of the study report the results of this trial will be either submitted for publication and/or posted in a publicly accessible database of clinical trial results.

## **12 Protocol adherence**

Investigators ascertain they will apply due diligence to avoid protocol deviations. Under no circumstances should the investigator contact Novartis or its agents, if any, monitoring the trial to request approval of a protocol deviation, as requests to approve deviations will not be granted.

This protocol defines the study objectives, the study procedures and the data to be collected on study participants. Under no circumstances should an investigator collect additional data or conduct any additional procedures for any research related purpose involving any investigational drugs.

If the investigator feels a protocol deviation would improve the conduct of the study this must be considered a protocol amendment, and unless such an amendment is agreed upon by Novartis and approved by the IRB/IEC it cannot be implemented. All significant protocol deviations will be recorded and reported in the CSR.

### **12.1 Protocol Amendments**

Any change or addition to the protocol can only be made in a written protocol amendment that must be approved by Novartis, Health Authorities where required, and the IRB/IEC. Only amendments that are required for patient safety may be implemented prior to IRB/IEC approval. Notwithstanding the need for approval of formal protocol amendments, the investigator is expected to take any immediate action required for the safety of any patient included in this study, even if this action represents a deviation from the protocol. In such cases, Novartis should be notified of this action and the IRB/IEC at the study site should be informed within 10 working days or less, if required by local regulations.

## 14 Appendix 1: Clinically notable laboratory values

Clinically notable laboratory abnormalities for selected tests based on a percent change from baseline (screening laboratory):

### Hematology

RBC count*	>50% increase, >25% decrease
Hemoglobin	>50% increase, >25% decrease
Hematocrit	>50% increase, >25% decrease
WBC count	>100% increase, >50% decrease
Platelet count	>100% increase, >50% decrease

### Blood Chemistry

ALT (SGPT)	See Section 7.3 Liver safety monitoring
AST (SGOT)	See Section 7.3 Liver safety monitoring
BUN	>100% increase
Creatinine	>100% increase
Total bilirubin	See Section 7.3 Liver safety monitoring
Alkaline phosphatase	>100% increase
Potassium	>25% increase, >25% decrease
Calcium*	>20% increase, >20% decrease
Uric acid*	>100% increase

\*Collected in the laboratory substudy only

## 15 Appendix 2: Liver event and laboratory trigger definitions and follow-up requirements

**Table 15-1** Definitions of liver events, which cannot be solely explained by apparent cardiac decompensation as the underlying cause (i.e., another etiology is suspected to cause or contribute to this event)

	Definition/ threshold
Liver laboratory triggers	

• <math>3 \times \text{ULN} < \text{ALT/AST} \leq 5 \times \text{ULN}</math>

• <math>1.5 \times \text{ULN} < \text{TBL} \leq 2 \times \text{ULN}</math>

Liver events	

• <math>\text{ALT or AST} > 5 \times \text{ULN}</math>

• <math>\text{ALP} > 2 \times \text{ULN}</math> (in the absence of known bone pathology)

• <math>\text{TBL} > 2 \times \text{ULN}</math> (in the absence of known Gilbert syndrome)

• Potential Hy's Law cases (defined as <math>\text{ALT or AST} > 3 \times \text{ULN}</math> and <math>\text{TBL} > 2 \times \text{ULN}</math> (mainly conjugated fraction) without notable increase in ALP to <math>> 2 \times \text{ULN}</math>)

• Any clinical event of jaundice for (or equivalent term)

• <math>\text{ALT or AST} > 3 \times \text{ULN}</math> accompanied by (general) malaise, fatigue, abdominal pain, nausea, or vomiting or rash with eosinophilia

• Any adverse event potentially indicative of liver toxicity*

\* These events cover the following: hepatic failure, fibrosis and cirrhosis, and other liver damage-related conditions; the non-infectious hepatitis; the benign, malignant and unspecified liver neoplasms

**Table 15-2 Follow Up Requirements for liver events and laboratory triggers, which cannot be solely explained by apparent cardiac decompensation as the underlying cause (i.e., another etiology is suspected to cause or contribute to this event)**

Criteria	Actions required	Follow-up monitoring
Potential Hy's Law case a	Discontinue the study drug immediately Hospitalize, if clinically appropriate Establish causality Complete liver CRF	ALT, AST, fractionated bilirubin d , Alb, PT/INR, ALP and $\gamma$ GT until resolution c (frequency at investigator discretion)
ALT or AST		
> 8 x ULN	Discontinue the study drug immediately Hospitalize if clinically appropriate Establish causality Complete liver CRF	ALT, AST, fractionated bilirubin d , Alb, PT/INR, ALP and $\gamma$ GT until resolution c (frequency at investigator discretion)
> 5 to $\leq$ 8 x ULN	Repeat LFT within 48 hours If elevation persists continue follow-up monitoring If elevation persists for more than 2 weeks , discontinue the study drug Establish causality Complete liver CRF	ALT, AST, fractionated bilirubin d , Alb, PT/INR, ALP and $\gamma$ GT until resolution c (frequency at investigator discretion)
> 3 x ULN accompanied by symptoms b	Discontinue the study drug immediately Hospitalize if clinically appropriate Establish causality Complete liver CRF	ALT, AST, fractionated bilirubin d , Alb, PT/INR, ALP and $\gamma$ GT until resolution c (frequency at investigator discretion)
> 3 to $\leq$ 5 x ULN (patient is asymptomatic)	Repeat LFT within the next week If elevation is confirmed, initiate close observation of the patient	Investigator discretion Monitor LFT within 1 to 4 weeks
ALP (isolated)		
> 2 x ULN In the absence of known bone pathology	Repeat LFT within 48 hours If elevation persists, establish causality Complete liver CRF	Investigator discretion Monitor LFT within 1 to 4 weeks or at next visit
TBL (isolated)		

Criteria	Actions required	Follow-up monitoring
> 2 x ULN (in the absence of known Gilbert syndrome)	Repeat LFT within 48 hours If elevation persists, discontinue the study drug immediately Hospitalize if clinically appropriate Establish causality Complete liver CRF	ALT, AST, fractionated bilirubin d , Alb, PT/INR, ALP and γGT until resolution c (frequency at investigator discretion) Test for hemolysis (e.g., reticulocytes, haptoglobin, unconjugated [indirect] bilirubin)
> 1.5 to ≤ 2 x ULN (patient is asymptomatic)	Repeat LFT once or twice in the week. If elevation is confirmed, initiate close observation of the patient	Investigator discretion Monitor LFT within 1 to 4 weeks or at next visit
Preferred terms		
Jaundice	Discontinue the study drug immediately Hospitalize the patient Establish causality Complete liver CRF	ALT, AST, fractionated bilirubin d , Alb, PT/INR, ALP and γGT until resolution c (frequency at investigator discretion)
"Any AE potentially indicative of a liver toxicity"	Medically significant Consider study drug interruption or discontinuation Hospitalization if clinically appropriate Establish causality Complete liver CRF	Investigator discretion

\* These events cover the following: hepatic failure, fibrosis and cirrhosis, and other liver damage-related conditions: the non –infectious hepatitis: the benign, malignant and unspecified liver neoplasms

a Elevated ALT/AST > 3 x ULN and TBL > 2 x ULN but without notable increase in ALP to > 2 x ULN

b (General) malaise, fatigue, abdominal pain, nausea, or vomiting, or rash with eosinophilia

c Resolution is defined as an outcome of one of the following: (1) return to baseline values, (2) stable values at three subsequent monitoring visits at least 2 weeks apart, (3) remain at elevated level after a maximum of 6 months, (4) liver transplantation, and (5) death.

d Fractionated bilirubin includes testing for total bilirubin, direct bilirubin, and indirect bilirubin.

## 16 Appendix 3: Physician assessment of signs and symptoms

The following criteria are to be used to assess patient's signs and symptoms of heart failure.

Exertional Dyspnea: The subject should be queried as to the extent of dyspnea noted over the preceding 1-3 hours as follows:

0	No exertional dyspnea (NYHA Class I equivalent)
1	Mild exertional dyspnea, occurring with moderate exertion (climbing stairs or equivalent-NYHA Class II equivalent)
2	Moderate exertional dyspnea, occurring with only mild exertion (walking-NYHA Class III equivalent)
3	Severe exertional dyspnea, occurring at rest (NYHA Class IV)

Orthopnea: The subject should be observed after being in the lowest recumbent position for 10-15 minutes or queried in order to determine the minimum number of "pillows" required to obtain/maintain comfort while supine. This should be graded on a 0 - 4 scale as follows:

0	Comfortable with no pillow or very minimal elevation of head
1	Comfortable with no less than one pillow to elevate head (approx 10 cm elevation)
2	Comfortable with no less than two pillows to elevate head (approx 20 cm elevation)
3	Comfortable with head no less than at 30 degree elevation

Rales: Auscultation of the lungs applying a 4-point scale:

0	No rales heard, either moist or dry, after clearing with cough anywhere in the lung fields
<1/3	Moist or dry rales heard in the lower 1/3 of either or both lung fields that persist after a cough in attempt to clear
1/3-2/3	Moist or dry rales heard throughout the lower half to 2/3 of either or both lung fields
>2/3	Moist or dry rales heard throughout both lung fields

Jugular venous pulse (JVP): With the subject supine at approximately a 45-degree angle, examination of the JVP is performed and the estimation, in cm H2O, is converted into one of 3 categories:

<6 cm H 2 O	Complete absence of discernable venous wave throughout respiratory cycle above the clavicle, even with hepatic compression (HJR)
6-10 cm H 2 O	Venous wave detectable above the clavicle, at least during expiration and possibly throughout respiratory cycle but less than 4 cm above the clavicle (<10 cm H 2 O). Presence of venous wave only with mild HJR should be graded in this category.
>10 cm H 2 O	Presence of venous wave throughout respiratory cycle with wave sometimes ≥ 4 cm H 2 O above clavicle and typically increased with HJR. Patients with values of 6-10 cm H 2 O and positive HJR should be graded in this category.
NA	Examination could not be performed/result unobtainable

Peripheral Edema, Pre-sacral Edema: Edema should be examined in any dependent area including the lower extremities or the sacral region. The range to be applied is 0 - 3 (4 point scale).

0	The complete absence of edema, as determined by applying mild digital pressure in all dependent areas and failing to elicit any indentation of skin and subcutaneous tissues.
1+	Detection of limited areas where mild digital pressure elicits an indentation of skin and subcutaneous tissues that resolves over approximately 10-15 seconds. Edema of this grade is typically limited to only the lower extremities or only the sacrum, not both.
2+	Detection of moderate surface area in one or both areas (sacrum and lower extremities) where indentations of skin and subcutaneous tissues are easily created with limited pressure and these indentations disappear slowly (15-30 seconds or more).
3+	Large areas of lower extremities (and sacrum if subject has been recumbent), often to mid-calf or higher, having easily produced and slowly resolving (more than 30 seconds) indentations. This extent of edema is sometimes associated with acute or subacute skin changes including weeping of skin and/or skin break down.

Patient's assessment of dyspnea: Patient should be asked to assess their level of shortness of breath compared to admission using a scale from 0 to 10 where 0=none to 10=very very severe (maximal).

Table 2-5 Primary, secondary and exploratory variables	15
Table 2-6 IV loop diuretics.....	23
Table 2-7 Safety risk and event of interest search specification	27
Table 2-8 Criteria for evaluating liver toxicity.....	31
Table 2-9 Nominal one-sided alpha at 70% randomized subjects accrued if CVD is rejected	34
Table 2-10 Assumed effect sizes for worsening heart failure and the key secondary efficacy variables on power calculation.....	36
Table 2-11 Powers (unconditional) of primary and key secondary variables on selected scenarios	36

Document History – Changes compared to previous version of RAP module 3.

Version	Date	Changes
Amendment 1	13-Aug-2015	
 -add the testing strategy for WHF and secondary endpoints in case of early stopping -add sensitivity analysis for WHF using logistic regression -add substudy population definition
Amendment 2	06-Feb-2017	
 - Clarify the method of mapping discharge visit to scheduled visits if scheduled visits are missing - Update the list of countries that recruited subjects (Table 2-3) - Remove subgroup category of lymphocytes and education level in Table 2-4 - Use FAS in section 2.1.9 – study medication summary. - Align presentation of non-IV concomitant medications with RELAX-AHF - Clarify definition of the censoring date for death endpoints (Adjudicated CV death, adjudicated all cause death) for patients who withdrew consent in countries where vital status data is publically available, in accordance with local laws and regulations - Clarify use of discharge date as the reference date for endpoint time to the composite endpoint of CV death or rehospitalization due to HF/RF during a follow-up period of 30 days post-discharge - Clarify the statistical method used for subgroup analysis of length of stay (LOS). Clarify the imputation rule for missing discharge information to align with RELAX-AHF - Clarify the imputation of signs and symptoms through Day 5 for subjects with WHF or died at hospital to align with RELAX-AHF - Addition of two new tables per ClinicalTrials.gov and EudraCT requirement -Update Safety risk and event of interest search specification (Table 2-7) - Clarify the ECG analysis population - Update the ECG categorical analysis, add analysis of newly occurring abnormalities in ECG morphology and remove ECG shift table to enable comprehensive assessment - Update liver function categorical analysis (Table 2-8)
Amendment 3	03-Mar-2017	
 - Add a new protocol deviation “ Site closed down for GCP reasons” leading to exclusion from the FAS and PPS -Subjects without valid written informed consent will be excluded from all analysis populations. - Remove covariate lymphocytes (%) from covariate-adjusted sensitivity analysis of CV death because of a number of missing values at baseline

List of abbreviations

ACE	Angiotensin Converting Enzyme
ACM	All-cause mortality
AE	Adverse Event
AHF	Acute Heart Failure
ALP	Alanine Phosphatase
ALT	Alanine Aminotransferase
ARB	Angiotensin-II Receptor Blocker
AST	Aspartate Aminotransferase
ATC	Anatomical Therapeutic Chemical
BNP	Brain Natriuretic Peptide
BPDE	Blood pressure decrease event
BUN	Blood Urea Nitrogen
CBPDE	Confirmed blood pressure decrease event
CCU	Coronary care unit
CEC	Clinical Endpoints Committee
CI	Confidence interval
CPK	Creatine Phosphokinase
CRF	Case Report Form
CSR	Clinical Study Report
█	█
CV	Cardiovascular
CVD	CV death
CVDR	CV death or rehospitalization due to heart failure or renal failure
CWHF	Clinical Worsening Heart Failure
dL	Deciliter
DMC	Data Monitoring Committee
DRE	Disease-related event
ECG	Electrocardiogram
EF	Ejection fraction
eGFR	Estimated Glomerular Filtration Rate
FAS	Full Analysis Set
GCP	Good Clinical Practice
HF	Heart failure
ICU	Intensive Care Unit
ITT	Intent-to-treat
IV	Intravenous
kg	Kilogram
LFT	Liver Function Toxicity
LOS	Length of hospital stay
LPLV	Last Patient Last Visit

LSM	Least-square Mean
MAP	Master Analysis Plan
MedDRA	Medical Dictionary for Regulatory Activities
MRA	Mineralocorticoid receptor antagonist
mg	Milligram
min	Minute
mL	Milliliter
mmHg	Millimeters mercury
NYHA	New York Heart Association
OF	O'Brien-Fleming
PASS	Physicians Assessment of Signs and Symptoms
PD	Protocol Deviation
PPS	Per Protocol Set
PT	Preferred Term
RAN	Randomized Set
RAP	Report and Analysis Preparation
RBC	Red Blood Cell
SAE	Serious adverse event
SAF	Safety Set
SAS	Statistical Analysis System
SBP	Systolic Blood Pressure
SCR	Screened Set
SGOT	Glutamic Oxaloacetic Transaminase
SGPT	Glutamic Pyruvic Transaminase
sMDRD	Simplified Modification of Diet in Renal Disease
SMQ	Standardized MedDRA Query
SOC	System Organ Class
TBL	Total Bilirubin
ULN	Upper Limit of Normal
WHF	Worsening heart failure
WHO-DD	World Health Organization Drug Dictionary
µg	Microgram

1 Introduction

The CRLX030A2301 study (also referred to as RELAX-AHF-2) aims to evaluate the efficacy, safety and tolerability of intravenous infusion of 30 µg/kg/day serelaxin for 48 hours, when added to standard therapy. Data from this study is intended to replicate the reduction in mortality in AHF patients observed in the RELAX-AHF study.

The purpose of this document is to outline the planned analyses to be completed to support the completion of the Clinical Study Report (CSR) for RELAX AHF-2.

2 Statistical methods planned in the protocol and determination of sample size

Data will be analyzed according to the data analysis section 10 of the study protocol which is available in [Appendix 16.1.1 of the CSR](#).

All nominal time points will be used for analysis; actual assessment times will not be used to reclassify the time point at which a measure was taken. Time-to-event analyses will be based on actual dates (time) reported.

All references to index hospitalization refer to the initial hospitalization for AHF.

Unless specified, descriptive statistics indicates mean, median, standard deviation, minimum and maximum will be presented for continuous variables; the number and percentage of subjects in each category will be presented for categorical variables for each treatment group and all subjects (total).

2.1 Subject and treatment

2.1.1 Analysis population

The following analysis populations will be defined for statistical analysis:

- **Screened set (SCR)** – All subjects who signed the informed consent. The SCR includes only *unique screened subjects*.
- **Randomized set (RAN)** - All subjects who received a randomization number, regardless of receiving trial medication.
- **Safety set (SAF)** - All subjects who received any amount of study drug and have at least one post-baseline safety assessment. Of note, the statement that a subject had no adverse events also constitutes a safety assessment. Subjects will be analyzed according to treatment received. Subjects who received any amount of serelaxin will be included in the serelaxin treatment group.
- **Full analysis set (FAS)** - All subjects in the RAN population who were not misrandomized subjects*. Following the intent-to-treat (ITT) principle, subjects are analyzed according to the treatment they have been assigned to at the randomization. Further exclusions from the FAS were only justified in exceptional circumstances

(e.g., site closed down for GCP reasons). The determination of which patients were excluded from the FAS is made in a blinded manner before the database lock.

* Misrandomized subjects are those who have not been qualified for randomization, have been inadvertently randomized into the study and who did not take study drug. Misrandomized subjects are defined as cases where IRT calls were made by the site either prematurely or inappropriately prior to confirmation of the subject’s final randomization eligibility and double-blind medication was not administered to the subject. These subjects should subsequently be discontinued from the study.

- **Per protocol set (PPS)** – all subjects in the FAS who received any amount of study medication and have no major protocol deviations.

Subjects without valid written informed consent will be excluded from all analysis populations.

Laboratory substudy and electrocardiogram (ECG) substudy populations will be defined for subjects participating laboratory or ECG substudy with informed consent.

2.1.2 Protocol deviation (PD)

All cases of prospectively defined protocol deviations (PD) will be identified prior to clinical database lock/unblinding and entered into a dedicated data panel as part of the locked database. Certain deviations may stipulate that data collected from the subjects will be excluded from PPS. This PPS is used to assess robustness of the primary and key secondary analysis results.

All exceptional cases, problems and the final decisions on the allocation of subjects to populations will be fully defined and documented before data base lock (in particular before breaking the blind where applicable) and will be fully identified and summarized in the clinical study report.

Criteria defining protocol deviations are referenced in the “PD specs and edit check’ tab of Edit Check Specification document. Protocol deviations will be classified into 5 categories as appropriate:

- Selection criteria not met
- Subject not withdrawn as per protocol
- Treatment deviation
- Prohibited concomitant medication
- Other

The major protocol deviations resulting in exclusion of subjects from an analysis population are outlined in the table below:

Table 2-1 Protocol deviations resulting in exclusion of subjects from analysis populations

PD category	Deviation	Excluding from analysis set			
		RAN	FAS	SAF	PPS

PD category	Deviation	Excluding from analysis set			
		RAN	FAS	SAF	PPS
Selection criteria not met	Missing informed consent (Inclusion criteria #1)	x	x	x	x
	Patient hospitalized for reasons of non-AHF event (inclusion criteria #3)				x
	Systolic BP <125 mmHg at the start and/or at the end of screening (inclusion criteria #4)				x
	Time from presentation to randomization >16 hours (inclusion criteria #5)				x
	Dose of IV furosemide between presentation and start of screening is < 40 mg (inclusion criteria #6)				x
	eGFR is <25 or > 75 mL/min/1.73m ² at screening (inclusion criteria #7)				x
	Dyspnea is primarily due to non-cardiac causes (exclusion criteria #1)				x
	Sepsis or active infection requiring IV anti-microbial treatment reported at screening (exclusion criteria #4)				x
	AHF is due to significant arrhythmias (exclusion criteria #6)				x
	Pre-randomization eGFR < 25 mL/min/1.73m ² or ongoing or planned dialysis or ultrafiltration at screening (exclusion criteria #7)				x
Treatment derivation	Serelaxin infusion administered in diluent other than the recommended 5% dextrose bags				x
	Wrong study drug kit administered or wrong dose administered				x
	Subject misrandomized		x	x	x
Other	Site closed down for GCP reasons		x		x

In addition, deviations not defined in the protocol resulting in exclusion of subjects from an analysis population are outlined in the table below.

Table 2-2 Non-protocol deviation criteria resulting in exclusion of subjects from analysis populations

Criterion	Excluding from analysis set			
	RAN	FAS	SAF	PPS
Subject randomized but not receiving any dose of double-blind study medication			x	x

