### 4.1 Inclusion criteria

Patients eligible for inclusion in this study have to fulfill **all** of the following criteria:

1. Written informed consent must be obtained before any study-specific assessment is performed\*
2. Male or female  $\geq 18$  years of age, with body weight  $\leq 160$  kg
3. Hospitalized for AHF with the anticipated requirement of intravenous therapy (including IV diuretics) for at least 48 hours; AHF is defined as including all of the following measured at any time between presentation (including the emergency department) and the end of screening:
  - Persistent dyspnea at rest or with minimal exertion at screening and at the time of randomization, despite standard background therapy for acute heart failure including the protocol required intravenous furosemide of at least 40 mg total (or equivalent).
  - Pulmonary congestion on chest radiograph
  - BNP  $\geq 500$  pg/mL or NT-proBNP  $\geq 2,000$  pg/mL; for patients  $\geq 75$  years of age or with current atrial fibrillation (at the time of randomization), BNP  $\geq 750$  pg/mL or NT-proBNP  $\geq 3,000$  pg/mL \*\*\*
4. Systolic BP  $\geq 125$  mmHg at the start and at the end of screening
5. Able to be randomized **within 16 hours** from presentation to the hospital, including the emergency department\*\*
6. Received intravenous furosemide of at least 40 mg total (or equivalent) at any time between presentation (this includes outpatient clinic, ambulance, or hospital including emergency department) and the start of screening for the study for the treatment of the current acute HF episode. Time from presentation to start of furosemide administration must be less than 6 hours.
7. Impaired renal function defined as an eGFR\*\*\* between presentation and randomization of  $\geq 25$  and  $\leq 75$  mL/min/1.73m^2, calculated using the sMDRD equation

*\* Patient assessments of AHF that are per current local institutional/hospital standard protocol or part of routine clinical care are allowed before signing informed consent, and can be used to support patient screening.*

*\*\* Presentation starts as the earliest of (1) time of presentation at either the ER/ED, ICU/CCU or ward, (excludes EMS or other pre-hospital care); or (2) time of first IV loop diuretic prior to arrival at the hospital (this includes outpatient clinic, ambulance, or hospital including emergency department) for the current acute HF episode.*

*\*\*\*Assessed based on local laboratory*

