11. Severe aortic insufficiency or severe mitral regurgitation for which surgical or percutaneous intervention is indicated.

12. Documented, prior to or at the time of randomization, restrictive amyloid myocardiopathy, OR acute myocarditis or hypertrophic obstructive, restrictive, or constrictive cardiomyopathy (does NOT include restrictive mitral filling patterns seen on Doppler echocardiographic assessments of diastolic function).
13. Current (within 2 hours prior to randomization) or planned (through the completion of study drug infusion) treatment with any IV vasoactive therapies, including vasodilators (including nesiritide), positive inotropic agents and vasopressors, or mechanical support (endotracheal intubation, mechanical ventilation; intra-aortic balloon pump or any ventricular assist device; hemofiltration, ultrafiltration or dialysis), with the exception of IV furosemide (or equivalent diuretic), or IV nitrates at a dose of  $\leq 0.1$  mg/kg/hour if the patient has a systolic BP  $>150$  mmHg at the start of screening.
14. Any major solid organ transplant recipient or planned/ anticipated organ transplant within 1 year
15. Major surgery, including implantable devices (e.g. ICD, CRT), or major neurologic event including cerebrovascular events, within 30 days prior to screening
16. History of malignancy of any organ system (other than localized basal cell carcinoma of the skin), treated or untreated, within the past year with a current life expectancy less than 1 year due to the malignancy.
17. Pregnant or nursing (lactating) women, where pregnancy is defined as the state of a female after conception and until the termination of gestation, confirmed by a positive hCG laboratory test
18. Women of child-bearing potential, defined as all women physiologically capable of becoming pregnant, unless they are using highly effective methods of contraception during dosing of study treatment plus 5 days after cessation of study drug. Highly effective contraception methods include:
  - Total abstinence (when this is in line with the preferred and usual lifestyle of the subject). Periodic abstinence (e.g., calendar, ovulation, symptothermal, post-ovulation methods) and withdrawal are not acceptable methods of contraception

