2.1.10.1 IV loop diuretic medications

IV loop diuretic medications include the following:

- Bumetanide

- Etacrynic acid/Ethacrynic acid
- Furosemide
- Torasemide/Torseamide

The number and percentage of subjects using IV loop diuretic medications will be summarized for each of the time periods: Hour 24/Day 1 to end of study, Hour 0/Day 1, 24 hours/Day 1, 48 hours/Day 2, Day 3, Day 4, Day 5, and Discharge. Each time point reflects medication use within the preceding 24 hours.

The average total daily dose for each medication will also be presented at reported time point. In addition, cumulative use reported at 48 Hours (24 hours/Day 1 and 48 hours/Day 2), and at Day 5 (from 24 hours/Day 1 to Day 5) in furosemide equivalent (mg) will be summarized. The calculation of furosemide equivalents (mg) for Bumetanide, Ethacrynic acid/Ethacrynic acid and Torsemide/Torseamide acid are actual dose (mg) multiplied by constant 40, 0.8, or 2, respectively. For subjects who die before Day 5, the minimum of 2 times of the last recorded dose and 160 mg will be assumed for every day from the date of death up to and including Day 5.

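### The SAP's per-protocol exclusion for background diuretic counts furosemide only, although the inclusion criterion it cites also accepts an equivalent dose of another agent

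*SAP*

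**What the plan says.** Protocol Section 4.1, criterion #6, requires of each patient: "Received intravenous furosemide of at least 40 mg total (or equivalent) at any time between presentation" and the start of screening. The synopsis and Sections 3.1 and 5.5.7 likewise allow an equivalent.

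SAP Section 2.1.2, Table 2-1, turns this criterion into a PPS exclusion: "Dose of IV furosemide between presentation and start of screening is < 40 mg (inclusion criteria #6"). The row mentions no equivalent.

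SAP Section 2.1.10.1 lists four IV loop diuretics (bumetanide, ethacrynic acid, furosemide, torasemide). It converts the three others to furosemide equivalents; the doses "are actual dose (mg) multiplied by constant 40, 0.8, or 2, respectively" for bumetanide, ethacrynic acid and torasemide. The factors are given for the concomitant-medication summary, and Table 2-1 does not refer to them.

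On vasoactive therapy, Protocol Section 4.2, exclusion #13, bars "Current (within 2 hours prior to randomization) or planned (through the completion of study drug infusion) treatment with any IV vasoactive therapies" or mechanical support. Its exceptions are IV furosemide or an equivalent diuretic, and IV nitrates up to a stated rate in patients above a stated systolic pressure. SAP Section 2.1.2 names "Prohibited concomitant medication" as one of five deviation categories. Neither Table 2-1 nor Table 2-2 has a row for that category or for exclusion #13. Table 2-1 does remove patients with "ongoing or planned dialysis or ultrafiltration at screening (exclusion criteria #7").

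The same SAP section gives the PPS the role of checking the robustness of the primary and key secondary results, and refers to an Edit Check Specification for the criteria that define deviations.

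**The concern.** A per-protocol set should remove patients who broke the protocol and keep those who followed it. The furosemide row can do the reverse: a patient who satisfied criterion #6 with another loop diuretic has a furosemide dose of zero and is classed as a major deviator. Anyone using the PPS result to judge robustness would then be looking at a set narrowed by choice of diuretic, not by adherence.

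The second matter is weaker. The protocol restricts IV vasoactive drugs and mechanical support at entry in three places (Sections 4.2, 5.5.7 and 5.5.8), yet a breach carries no listed PPS consequence except for dialysis and ultrafiltration. The restriction touches a primary endpoint: under Protocol Section 6.4.1, worsening heart failure (WHF) can be established by starting or up-titrating IV heart-failure drugs or by starting mechanical support. A patient already on one of these at entry cannot have that same therapy started.

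**Working it through.** The plan gives no figure on this point to reproduce. The check sets the criterion beside the row that enforces it, using the SAP's own factors.

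**Step 1. Dose of each agent equal to 40 mg furosemide.** Equivalent = actual dose × factor, so the dose needed = 40 / factor.

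- Bumetanide, factor 40: 40 / 40 = 1 mg
- Ethacrynic acid, factor 0.8: 40 / 0.8 = 50 mg
- Torasemide, factor 2: 40 / 2 = 20 mg

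**Step 2. Apply both rules to the same patients.**

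| IV loop diuretic before screening | Furosemide equivalent | Criterion #6 | Furosemide dose in the row | PPS by the row as written |
|---|---|---|---|---|
| Furosemide 40 mg | 40 mg | met | 40 mg | kept |
| Bumetanide 1 mg | 40 mg | met | 0 mg | removed |
| Torasemide 20 mg | 40 mg | met | 0 mg | removed |
| Furosemide 20 mg + bumetanide 0.5 mg | 20 + 0.5 × 40 = 40 mg | met | 20 mg | removed |

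The last line shows that mixed treatment is affected too.

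**Step 3. Scale, by assumption only.** The documents do not give the share of patients who met #6 without 40 mg of furosemide itself. To show what a given share would do, take 6,800 patients (SAP Section 2.5), 329 / 0.6 = 548 CV deaths (329 being the 60% interim count), the final boundary Z = 2.072 and HR 0.78. Power is approximately Φ(√(D/4) × |ln 0.78| − 2.072). With D = 548 this is 79.9%. Assume events are lost in proportion to patients:

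| Assumed share | Patients | CV deaths left | Power |
|---|---|---|---|
| 1% | 68 | 543 | 79.5% |
| 5% | 340 | 521 | 77.7% |
| 10% | 680 | 494 | 75.4% |
| 20% | 1,360 | 439 | 70.2% |

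The PPS will be smaller than 6,800 for other reasons, so these are reference values, not forecasts.

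**Step 4. Exclusion #13 against the tables.** Of the 23 exclusion criteria in Protocol Section 4.2, Table 2-1 cites four: #1, #4, #6 and #7. Through #7 it removes dialysis and ultrafiltration at screening, which are also part of #13. What remains without a row is IV vasoactive drugs outside the stated exceptions, intubation or ventilation, balloon pump and ventricular assist device. Use after randomization is a separate matter. Protocol Sections 5.5.6 and 5.5.8 allow it, and Section 6.4.1 can count it as a WHF event.

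**The case against.** **The row may be shorthand.** It cites criterion #6, which contains the equivalence. Other rows are abbreviated as well; the arrhythmia row lists none of the rhythms in exclusion #6. The defining criteria sit in the Edit Check Specification, which was not supplied. This stands to the extent that nobody can say from these documents that eligible patients will in fact be removed. It does not remove the need to act, because the dose limit is the whole content of the row. Nor is the table fully aligned with the current protocol: its row for exclusion #1 still says primarily due to non-cardiac causes, a qualifier that current exclusion #1 does not have.

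**Table 2-1 is a chosen subset.** Nineteen of the 23 exclusion criteria have no row, and the category for subjects not withdrawn as per protocol is empty too. This stands: leaving out #13 is not shown to be an error. Background use is also examined elsewhere, through the subgroup by IV nitrate use at randomization (SAP Table 2-4), the summary of other IV drugs (SAP Section 2.1.10.2) and the nitrate interaction (Protocol Section 10.5.2).

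**Stronger readings that a reader might infer.** None is supported.

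- *Every breach of exclusion #13 stays in the PPS.* Dialysis and ultrafiltration at screening are removed through #7.
- *The PPS comparison is confounded.* Diuretic choice before screening and vasoactive use before randomization both precede treatment assignment. Selecting on them changes the precision and the population described, and does not by itself bias the randomized comparison.
- *The patients kept have a high risk of early death, or those dropped cluster by country or site.* The documents give no data on either.
- *The PPS fails as a test of treatment under the protocol.* It still enforces many entry and treatment rules, and the effect depends on unknown counts.

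**Conclusion.** The furosemide row does not match the criterion it cites and should be corrected. The mismatch can be read directly from the two texts. Its practical effect rests on two unknowns: whether the row is programmed as worded, and how many patients met #6 with another or mixed loop diuretic. The effect is confined to the supportive PPS analyses of the primary and key secondary endpoints. The full-analysis-set results, the alpha allocation and the stopping boundary do not change.

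The missing row for exclusion #13 is a reasonable addition or clarification, not a demonstrated mistake. It concerns use that is current or planned at entry, and the number of patients is unknown.

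**What to change.** Before database lock:

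1. Reword the Table 2-1 row to: *Total IV loop diuretic between presentation and start of screening < 40 mg furosemide equivalent (factors of Section 2.1.10.1)*. Align the Edit Check Specification with it.
2. Either add a PPS row for exclusion #13 as it applies at entry, or state why such a breach is not a major deviation. A new row should cover both parts of the criterion (current within 2 hours before randomization, or planned through the infusion) and carry its stated exceptions. It should not exclude on unplanned use after randomization, since that would select patients on a possible WHF outcome.

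The cost is one reworded row, one new row or a sentence of justification, and the matching edit checks. The conversion factors already exist, and SAP Amendment 3 added a deviation row to this same scheme. The sponsor should confirm that doses of the other loop diuretics are recorded for the period before screening. The first change can only keep more patients in the PPS; a new #13 row may remove some.
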